3.0 Purpose

The purpose is to evaluate the safety and effectiveness of Mobility+ enteral feeding system via this initial post-market study (510k clearance number K222678) in adults, a subset of the intended use population. This evaluation will be conducted in a prospective, single arm, non-randomized clinical study.

Hypothesis and Objectives

The study hypothesis is that Mobility+ meets its intended use, safely. The objectives are to evaluate the below primary and secondary endpoints, through execution of this protocol:

Endpoint	Detail	How it will be measured
Primary: Safety and Effectiveness of Mobility+	Evaluate participants who have received familiarization training can use device, according to IFU, to allow delivery of liquid nutrition to their feeding tube, in a real-life setting (home), safely (i.e. can execute critical device use tasks to allow feeding, without serious adverse events) and with effectiveness (i.e. using Mobility+ for the majority or all of their feeding sessions i.e. two daily feeds, minimum)	Phone communication and checklist (Appendix8)

Secondary: Usability of Mobility+	Evaluate Participant perspectives on mobility, ease of use and tolerance, with their current feeding system(s) and Mobility+	Participant perspectives surveys: Baseline (Appendix 4) End of study (Appendix 7)
	Evaluate changes in participant Quality of Life (QoL)	QoL survey at baseline (Appendix 5) and QoL question at end of study (Appendix 7)
	Estimate if participants consume similar average volume (and kcals) of feed/day during the study, compared to baseline	Collect descriptive data on estimated average feed volume and kcals consumed at baseline (Appendix 3) and at end of study (Appendix 8)

The outcome will be presented in a study report.

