8.5 Study Measurements

The study measurements which will be taken are detailed in Table 3 below:

Table 3: Study measurements

Baseline measurements:	
 Demographics (Appendix 3) Average volume and Kcals of feed consumed / day (Appendix 3) Quality of life measure (Appendix 5) Participant perspectives on mobility, ease of use (current system(s)) and feeding intolerance symptoms (Appendix 4)
Trial days	
 Tubing SKU check (Appendix 6)
Interim survey questions (Study Day 7)	
 Tubing SKU check, safety and effectiveness check, compliance and calorie intake check (Appendix 8)
End of study measurements (Study Day 14):	
 Quality of life question (Appendix 7) Participant perspectives on mobility and ease of use of Mobility+ system (Appendix 7) Note of tubing SKU used, safety and effectiveness check, compliance and calorie intake check, General end of study questions (wearing, wellbeing, future use etc.) (Appendix 7)

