14.0 Appendices

Appendix 1

Eligibility-Screening Log

Date:		
Operator(s) ID:		
Questions:	Answers:	
All answers to the following questions must be 'YES' for a candidate to be deemed eligible for this Study.		
1. Is the candidate at least 18 years of age?	YES 	NO 
2. Do they have a gastrostomy tube or jejunostomy tube?	YES 	NO 
3. Do they use a standard enteral feeding system (gravity bag, enteral nutrition pump, bolus or combination(s)?	YES 	NO 
4. Have they been on an enteral feeding regime for greater than or equal to 10 weeks?	YES 	NO 
5. Do they currently require greater than or equal to 500ml enteral nutrition every day ?	YES 	NO 
6. Do they tube feed either during the day or day and night ?	YES 	NO 
7. Is their clinical functional capacity adequate to enable them to participate fully in the study? (Determined by operator clinical judgement)	YES 	NO 
8. Is the patient mobile? (Determined by operator clinical opinion)	YES 	NO 
9. Do they currently use a commercially available enteral formula that is listed on the Mobility+ Flow Rate Guide?	YES 	NO 

Appendix 2
Screening Questionnaire

(Operator asks the Participant these questions)

Participant ID:						
Date:						
Operator(s) ID:						
Questions:	Answers:					
1. What type of feeding system(s) do you use?	GRAVITY BAG 	PUMP 	SYRINGE/BOLUS 	COMBINATION 		
If COMBINATION, please give detail						
2. What is the name of the enteral feed you use?	Brand:		Type:			
3. Do you feed during the day, at night or a combination of both?	DAY 	NIGHT 	COMBINATION 			
4. What volume (and kcals) of enteral nutrition do you typically consume over a 24 hour period? mls	 kcals			
5. How many feeding sessions do you have per day?					
6. How many hours do you typically infuse for over a 24 hour period? hours	 minutes			

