7. What flow rate do you typically use (i.e. per feeding, what ml of formula do you provide over how many minutes)?	0-50ml/hr 	50-100ml/hr 	100-150ml/hr 	UNSURE* 		
*Calculated Average Flow Rate:						
8. How many full feeding sessions do you miss a day?	0	1	2	3	4	Other
9. How many feeding sessions do you cut short each day?	0	1	2	3	4	Other
10. Are you able to swap from your current system to Mobility+ for a minimum of two daily feeds (operator calculates this volume using	YES 		NO 			

answer to Q.4 and Q.5) for a trial period of 5 -7 days, followed by 14 consecutive study days? *Note to operator: minimum device fill is 250ml (as per precautions in IFU)			
Operator Facing Questions			
11. Is the subject a suitable candidate for using Mobility+ based on their enteral feeding needs and alignment to the Mobility+ Flow Rate Guide (See giving set SKU decision tree for prescribing Mobility+ Figure 6)	YES 	NO 	
The candidates feed and flow rate needs mean the most appropriate tubing SKU to start them on during trial days is:			
440mm RED 	700mm BLUE 	1000mm GREEN 	1900mm WHITE 

Appendix 3
Demographics questionnaire

(Operator asks the Participant these questions where these elements are not already captured from Electronic Medical Records)

Questions:	Answers:	
Are you male/female?	Male 	Female 
What is your age? (years)	
What is your height (cm)? cm	
What is your weight (kg)? kg	
What is your diagnosis? Note: Operator selects a standard pathophysiological mechanism from list	 Malignancy  Mechanical Obstruction  GI Dysmotility  Hepato-biliary/Pancreatic  Mucosal Disease  Trauma/Injury  Neuro-degenerative Disease  Short Bowel Syndrome  Functional Disorder  Bariatric Surgery  Congenital/Developmental	
Are you working or studying (or both)?	Yes, I work, study or both 	No, I neither work or study 

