		

How strongly do you agree with the following statement? I would like to use the Mobility+ again.

Strongly Agree	Somewhat Agree	Neutral	Somewhat Disagree	Strongly Disagree
				

If you would like to use Mobility+ again, how often would you like to use it?

Every Day	Every Week	Every Month
		

Think about your overall wellbeing if you used Mobility+ for SOME/ALL of your tube feeding needs, in the long term. How would your wellbeing be then, compared to now?

Much Better	Somewhat Better	About the Same	Somewhat Worse	Much Worse
				

Would you pay out of pocket for the Mobility+?

YES	NO
	

How did you choose to wear the Mobility+ system?

- Crossbody bag**
- Handbag**
- Backpack**
- In clothing**
- Clipped onto belt/clothing**
- Other (Detail):**

Appendix 8

Appendix 8 - Phone communication check sheet (Study Day 7 and 14) - (Operator asks the Participant these questions)

Day 7

Day 7			
Questions:	Answers:		
Day 7 Safety & Effectiveness Check			
Are you able to use Mobility+ to successfully and safely provide enteral feeding?	 YES  NO		
Day 7 Compliance & Calorie Intake Check			
Consider your feed intake over the last 3 days (i.e. Study day 4, 5, 6).			
Questions:	Answers:		
What volume of enteral nutrition did you consume on average per day (i.e. over 24 hr)?	Volume Mobility+mls		
How many hours did you typically infuse for, on average/day? hours minutes		
How many feedings did you intend to take using Mobility+ , on average / day?feedings		
How many feedings were you able to take using Mobility+ , on average / day?feedings		
What was the average volume of enteral nutrition that you consumed per feeding with Mobility+?mls		
What time of the day did you provide feedings with Mobility+?	Morning  Afternoon  Evening  Night-time 		
Operator facing question: On average, did the participant take at least two daily feeds with Mobility+? If no, why not?	 YES		
	 NO		
Day 7 Tubing SKU check			
Study Day 7:			
SKU that participant is using:			

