440mm RED 	700mm BLUE 	1000mm GREEN 	1900mm WHITE 

Select one:	Stay on this SKU 	Trial  SKU 
Reason for changing:	
Intolerance  Taking too long to feed  Abdominal discomfort  Unable to tolerate feed 
	

Day 14

Day 14 Tubing SKU Check			
What giving set tubing are you using?			
440mm RED 	700mm BLUE 	1000mm GREEN 	1900mm WHITE 
Day 14 Safety & Effectiveness Check			
Are you able to use Mobility+ to successfully and safely provide enteral feeding?	YES 	NO 	
Day 14 Compliance & Calorie Intake Check			
Consider your feed intake over the last 3 days (i.e., Study Day 11, 12, 13).			
What volume of enteral nutrition did you consume on average per day (i.e. over 24 hr)	Volumemls	Volume Other Systemmls	
How many hours did you typically infuse for, on average/day? hours minutes	
How many feedings did you intend to take using Mobility+, on average / day? feedings		
How many feedings were you able to take using Mobility+, on average / day? feedings		
What was the average volume of enteral nutrition that you consumed per feeding with Mobility+?mls		
What time of the day did you provide feedings with Mobility+?	 Morning  Afternoon  Evening  Night-time		

Safety and Effectiveness of A Novel Enteral Feeding System:
Prospective Study Protocol
Page 41 of 49

NCT06173063

Operator facing question:	On average, did the participant take at least two daily feeds with Mobility+?	YES 	NO 
	If no, why not?	

Appendix 9

Adverse event classifications

The below figures from ISO 14155:2020 highlight the process to be followed to determine if an AE or device deficiency is one of the below:

- AE
- SAE
- ADE
- SADE
- ASADE
- USADE
- Device deficiency with SADE potential
- Device deficiency without SADE potential

Table F.1 — Categories of adverse events

Adverse events	Non-device-related	Device- or investigational procedure-related	
Non-serious	Adverse event (AE) ^a (3.2)	Adverse device effect (ADE) ^c (3.1)	

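### Baseline intake is asked as a typical day and study intake as a three-day average, with no rule for missed feeds, so the change in intake can be biased by an unknown amount in either direction

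*Protocol*

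**What the plan says.** Protocol Section 3.0 lists this secondary endpoint: "Estimate if participants consume similar average volume (and kcals) of feed/day during the study, compared to baseline". The measurement is descriptive: "Collect descriptive data on estimated average feed volume and kcals consumed at baseline", with Appendix 3 given as the baseline source and Appendix 8 as the end-of-study source. Table 3 in Section 8.5 repeats the baseline source: "Average volume and Kcals of feed consumed / day (Appendix 3". Section 8.10 also places the recording of calorie intake in Appendix 3.

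The text of Appendix 3 covers sex, age, height, weight, diagnosis, occupation and tube type. It shows no volume or kcal item. The only baseline intake question in the text is Appendix 2 item 4: "What volume (and kcals) of enteral nutrition do you typically consume over a 24 hour period". Item 8 of the same form asks "How many full feeding sessions do you miss a day", and item 9 asks how many sessions are shortened. Section 8.6 uses such answers to judge whether general compliance may be a problem. It does not link them to the baseline volume.

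Appendix 8 fixes the recall window on study. On Day 7 it is three days ("i.e. Study day 4, 5, 6"), and on Day 14 the instruction is "Consider your feed intake over the last 3 days (i.e., Study Day 11, 12, 13". The question that follows is "What volume of enteral nutrition did you consume on average per day (i.e. over 24 hr".

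The SAP sets out no intake analysis. Its Section 4 scores only the perspectives and quality-of-life ratings, and its Section 5 names a test without naming intake.

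**The concern.** In a single-arm before-and-after comparison, the change in intake means something only if both sides measure the same quantity. Here one side is a self-defined typical day and the other is a three-day average of what was taken. A participant may answer the first with the usual full regimen, or with what actually goes in after habitual misses. The form does not say which is wanted, and the misses are recorded elsewhere without a rule for combining them.

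Part of any baseline-to-study difference may therefore come from the change of question. Section 8.6 itself expects some incomplete compliance for reasons unrelated to the feeding system, so background misses are foreseeable. At stake is the statement that intake on Mobility+ was similar to, lower than or higher than usual intake.

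**Working it through.** **Plan figure.** The documents give no intake values, margin, standard deviation or miss rate, so there is no intake figure to reproduce. The enrolment target does reproduce, 20 / (1 − 0.20) = 25, but this point does not depend on it.

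**Set-up (assumptions).** True feeding behaviour is the same before and during the study. Let *m* be the share of regimen volume habitually missed, and *f* the share of those misses already reflected in the typical-day answer. The values of *m* below (5%, 10%, 20%) are illustrative.

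Baseline answer = 1 − *mf*. Expected study answer = 1 − *m*. Apparent change = (1 − *m*) / (1 − *mf*) − 1.

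| Share missed, *m* | *f* = 0 (full regimen reported) | *f* = 0.5 | *f* = 1 (already net) |
|---|---|---|---|
| 5% | −5.0% | 0.95/0.975 − 1 = −2.6% | 0% |
| 10% | −10.0% | 0.90/0.95 − 1 = −5.3% | 0% |
| 20% | −20.0% | 0.80/0.90 − 1 = −11.1% | 0% |

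**The other direction.** If item 4 is net of misses and the three-day window happens to contain none, the apparent change is 1/(1 − *m*) − 1: +5.3%, +11.1% and +25.0% for the same *m*. With independent misses and *s* sessions a day, a miss-free window has probability (1 − *m*)^(3*s*). At *m* = 10% this is 0.90^6 = 53% for two sessions a day and 0.90^12 = 28% for four. For one participant this is chance, and it averages out across participants if the windows are representative. It becomes a systematic rise if the days before a scheduled call are better than usual.

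**Coarseness of the window.** One missed session in three days lowers the average by 1/(3*s*): 16.7%, 11.1%, 8.3% and 5.6% at 2, 3, 4 and 6 equal sessions a day (assumed). SAP Section 7 reports outcome data on 17 participants, so a few such cases can move a mean.

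**Can the collected items repair it?** The obvious adjustment is item 4 − item 8 × (item 4 / item 5), where item 5 is sessions per day. Take four sessions of 250 ml with one always missed, so that true intake is 750 ml both before and during the study:

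- Item 4 answered as 1000 ml: unadjusted change 750/1000 − 1 = −25%. Adjusted baseline 1000 − 250 = 750 ml, change 0%.
- Item 4 answered as 750 ml: unadjusted change 0%. Adjusted baseline 750 − 187.5 = 562.5 ml, change 750/562.5 − 1 = +33%.

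The adjustment removes the artefact under one reading of item 4 and creates one under the other.

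**After matching the questions.** With the same wording and window at both times, *f* = 1 and the expected apparent change is 0% at any *m* when true intake is unchanged.

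**The case against.** A reader might infer that missed sessions can lower only the Mobility+ figure, so that the design builds in a false fall. The documents do not support that. Item 4 asks about consumption, not prescription, so habitual misses may already be in the answer, and an apparent rise is then possible. Appendix 2 does lend the full-regimen reading some weight: item 10 has the operator derive the volume of two daily feeds from items 4 and 5, which works if item 4 covers every session counted in item 5. That makes the reading plausible but does not establish it.

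A reader might also infer that a real change can never be told apart from the artefact. That goes too far. Screening records sessions, misses and shortened feeds, and Appendix 8 records intended and achieved Mobility+ feedings, so on-study shortfalls with the device are visible. A fall caused by feeds missed because of the device would be real. Only the different counting of background misses is an artefact.

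Two further objections stand in part:

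- Treating item 4 as the baseline is an inference. The protocol names Appendix 3, whose items may be taken from medical records. But Appendix 3 as printed has no intake field, and a record-based figure might be a prescribed amount, which would also differ from a three-day average.
- The endpoint is secondary and descriptive, with no margin or test, so no formal conclusion turns on it. This limits the weight of the point but does not remove the mismatch.

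**Conclusion.** The point holds as a mismatch of recall frames, combined with an unclear baseline source and no rule for missed or shortened sessions. The resulting change in intake can be biased by an unknown amount in either direction. If item 4 is answered as the full regimen and habits do not change, the false fall equals the share of volume habitually missed. The 5% to 20% shown is an assumed range, not an estimate for this trial. If the answer is already net of misses, the expected artefact is zero, with apparent rises possible when the three-day window is better than usual. The documents fix neither the sign nor the size. The impact is limited because the endpoint is secondary and descriptive, but a statement that intake was similar should not be made without disclosing the difference.

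**What to change.** **For the form.** At the clinic visit, ask the Appendix 8 intake question in the same words about the usual system(s): average volume and kcals actually consumed per 24 hours over the last 3 days, all systems combined. Name that item as the single baseline source in Sections 3.0, 8.5 and 8.10. Ask for kcals and for all systems on Days 7 and 14 too, since the text of those sheets shows no kcal field and only the Day 14 sheet shows a field for another system's volume. Keep item 4 for giving-set selection and the item 10 calculation. The cost is one added question at the visit, the matching fields on the two phone sheets, and a baseline that reflects three days rather than habitual intake.

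**For data already collected.** The SAP already reports outcomes, so the form change cannot help this dataset. State which source supplied the baseline and that the recall frames differ. Report the unadjusted change, and beside it the change from the baseline reduced by item 8 × (item 4 / item 5), labelled as one bound. It should not be called a correction: item 4 may already be net of misses, the numbered options in item 8 are whole sessions per day (someone who misses one session every three days may be entered as 0), and item 9 records no volume lost. The cost is one calculation from fields already held and two sentences in the report.

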2.0 Device Description

Device Description

The Mobility+ Enteral Feeding System (“Mobility+ System”) is a portable, lightweight, non-electronic, disposable enteral feeding system intended to deliver commercially available liquid nutrition formula to a patient, using a standard extension set (or feeding tube) with an ENFit® connector, in the clinical or home care settings.

The Mobility+ System delivers formula using a simple container system (“Feeding Pouch”) that has an internal elastomeric pump, filled by the user with formula, that gradually deflates once enabled. The deflation of the elastomeric pump generates a consistent, low pressure that gently pushes the formula from inside the elastomeric pump through the supplied tubing set (“Giving Set”) to the user’s extension set (or feeding tube), where the formula enters their digestive system through a surgically placed stoma. The progress of formula delivery is indicated by reductions in Feeding pouch inflation and weight, and completion of formula delivery is indicated by a cessation in formula flow out of the giving-set. Clinicians will consult product labelling to determine which giving-set patients should be guided to use, to provide for their individual flow rate needs. The system can be worn in a bag of choice, or in clothing, that can fit the system without kinking the tubing.

The Mobility+ System is self-contained, portable and does not require an external pump, power source, or IV pole. It is designed to provide the patient greater mobility and overall ease of use. It operates silently, avoiding noises which can prove distracting and sleep disrupting for patients requiring night-time feeding. It offers the overall simplicity of operation of gravity-fed systems without requiring gravity to deliver formula to the patient.

Figure 1: The Mobility+ System. Feeding Pouch (left), Filling Set and Giving Set (right);

The Mobility+ System is single patient use, disposable and intended for use over a 24-hour period. It has three primary components (Figure 1).

Primary components

The Feeding Pouch

The combined pump and reservoir of the Mobility+ System (Figure 2). It consists of a flexible protective sleeve with an internal silicone elastomeric pump.

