Which type of feeding tube do you have?	G-tube 	J-tube 

Appendix 4
Participant perspectives baseline survey

 Participant perspectives of current feeding system: Usability, mobility and ease of use

(Operator asks the Participant these questions)

During use of your current feeding system, how do you find these activities?	Very Difficult	Difficult	Neutral	Easy	Very Easy	
Moving from one room to another room						
Going up and down stairs						
Short walk (e.g., one block)						
Long walk (e.g., several blocks)						
Travelling in car/public transport						
Moderate intensity physical activities, such as: - Moving a table - Pushing a vacuum - Bowling - Playing golf						
Other daily activities (e.g., lifting or carrying groceries, household chores)						
Ability to sleep						
Socializing with friends/family						
During use of your current feeding system, how do you find working/studying or both? Please log as N/A if participant does neither.	Very Difficult	Difficult	Neutral	Easy	Very Easy	N/A
Note to operator: When scoring this questionnaire, assign points using the legend below. Very Difficult = 0 points, Somewhat Difficult = 1, Neutral = 2, Somewhat Easy = 3 and Very Easy = 4						
Thinking about your overall experience with your current system, how strongly do you	Strongly Disagree	Some-what Disagree	Neutral	Some-what Agree	Strongly Agree	

agree or disagree with the following statements?					
My current system is easy to use					
My current system is easy to carry					
The noise level of my current system during use (including alarms) is acceptable					
My current system allows me to feed discreetly					
I am satisfied with the overall performance of my current system					
Note to operator: When scoring this questionnaire, assign points using the legend below. Strongly Disagree = 0 points, Somewhat Disagree = 1, Neutral = 2, Somewhat Agree = 3 and Strongly Agree = 4					
Do you experience any of the following symptoms of feed intolerance while using your current feeding system?					
Gas/Bloating?	 Yes			 No	
If yes, is it mild, moderate, or severe?	 Mild	 Moderate	 Severe		
Abdominal Pain?	 Yes			 No	

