6.0 Supplemental Baseline data gathered

The following supplemental Baseline Data was gathered at patient enrollment (n=17).

Variables	
Diagnosis, n (%)	
Malignancy	13 (76.5)
GI Dysmotility	2 (11.8)
Bariatric Surgery	1 (5.9)
Functional Disorder	1 (5.9)
Occupation, n (%)	
Working/studying	6 (35.3)
Not working/studying	11 (64.7)
Type of Feeding Tube, n (%)	
G-Tube	14 (82.4)
J-Tube	3 (17.6)
Type of Feeding System before study, n (%)	
Infusion Pump	4 (23.5)
Bolus/Syringe	3 (17.6)
Gravity	7 (41.2)
Combination*	3 (17.6)
Daytime or Night-time Feeds n (%)	
Daytime Only	10 (58.8)
Nighttime Only	1 (5.9)
Both Day & Night-time	6 (35.3)

*Combination was Bolus/syringe, Gravity.

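### The sleep item has no not-applicable option or rule although 10 of 17 participants fed by day only at baseline, so its cohort change cannot be read as sleep during feeding

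*Protocol*

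**What the plan says.** Appendix 4 lists nine activities, rated from very difficult to very easy, under a stem tied to use of the current system: "feeding system, how do you find these activities". One of the nine is "Ability to sleep". Appendix 7 repeats the nine for Mobility+. On both forms the work/study question that follows has an N/A column and an instruction on when to use it. The nine activities have neither.

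Protocol 11.2 (Table 5) compares the overall score before and after, and allows comparison of single questions without requiring it. SAP 4.0 scores mobility separately from ease of use and averages each overall score over the cohort. It gives no rule for an item that does not apply.

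The table in SAP 6.0 is introduced with "The following supplemental Baseline Data was gathered at patient enrollment (n=17"). Its feeding-time rows are "Daytime Only 10 (58.8", "Nighttime Only 1 (5.9" and "Both Day & Night-time 6 (35.3" (the bracketed figures are percentages). Protocol 2.0 links sleep to overnight use: it describes silent operation, "avoiding noises which can prove distracting and sleep disrupting for patients requiring night-time feeding". On Study Days 7 and 14, Appendix 8 asks "What time of the day did you provide feedings with Mobility"; the SAP does not tabulate the answers.

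**The concern.** A person who feeds only by day does not normally sleep with the system running, so the literal question has no obvious answer for that person. With no N/A box, the likely responses are a rating of sleep in general, a neutral rating, or a rating coloured by overall liking of the device. The first two would dilute a real change in night feeders. The third could produce an apparent sleep benefit that no night feed caused. A cohort mean cannot tell these apart.

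The problem was foreseeable. Inclusion criterion 3 (Protocol 8.4) admits daytime-only feeders, and Appendix 2 Q3 records feeding time at screening. The forms already deal with the parallel case: 11 of 17 participants neither worked nor studied (SAP 6.0), and the work/study item has an N/A answer for them. At stake is whether a reported sleep improvement could be taken as support for a benefit that the device description attaches to night-time feeding.

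**Working it through.** **1. Reproduce the SAP's split.** 10/17 = 58.8%, 1/17 = 5.9%, 6/17 = 35.3%, and 10 + 1 + 6 = 17. All agree with SAP 6.0. Participants with any night feed at baseline: 1 + 6 = 7, and 7/17 = 41.2%.

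**2. Effect on the item's mean change.** Let d0 be the mean change in the 10 day-only feeders and d1 that in the 7 with night feeds. If all 17 answered, the cohort mean change is (10·d0 + 7·d1)/17, and the day-only share of it is 10·d0/(10·d0 + 7·d1). The documents give no item scores, so d0 and d1 are assumptions. Changes in points are the same on the protocol's 0–4 scale and the SAP's 1–5 scale.

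| d0 | d1 | Cohort mean change | Share from day-only feeders |
|---|---|---|---|
| 0 | 1.0 | 0.41 | 0% |
| 0.5 | 2.0 | 1.12 | 26% |
| 0.5 | 1.0 | 0.71 | 42% |
| 1.0 | 1.0 | 1.00 | 59% |
| 1.0 | 0.5 | 0.79 | 74% |

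The first row is pure dilution: 7/17 of the night feeders' change survives. In the last row the cohort mean (0.79) exceeds the night feeders' own change (0.5). The mean can therefore err in either direction.

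**3. Weight in the mobility score.** I take SAP 4.0's mobility measure to be the items rated from difficult to easy: the nine activities, plus work/study where it applies. The number of items k is then 10 or 9, and sleep is 1/10 or 1/9 of the score.

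**4. Effect on the mobility score, as a mean per item.** Compare the cohort mean change with the sleep item kept, and with it left out for the 10 day-only feeders.

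- Other mobility items rise by 1.0 and day-only sleep ratings stay flat: each day-only score changes by (k − 1)/k with the item and by 1 without it, a difference of 1/k. Over the cohort, leaving it out adds (10/17)(1/10) = 0.059 to (10/17)(1/9) = 0.065.
- Other items stay flat and day-only sleep ratings rise by 1.0: the same size with the opposite sign, −0.059 to −0.065.
- Only sleep changes, and only in night feeders: day-only scores change by 0 either way, so the difference is 0.

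In these cases the shift is at most about 0.07 points on a five-point scale.

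**The case against.** The strongest reply is that the plan poses no separate sleep question. The usability endpoint in Protocol 3.0 concerns mobility, ease of use and tolerance. Item comparisons are optional, the SAP defines no sleep analysis and reports no sleep result, and the sentence on night-time noise is device description. This largely stands, and it limits the point to how an item result may be reported and read. It does not remove the point, because Table 5 permits the comparison and the item enters the averaged mobility score in any case.

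A reader might infer that most of the item's before-after change comes from answers about a situation that never arose. The documents do not support that. Day-only feeders are most of the participants, but their share of the change is unknown; in the table above it runs from 0% to 74%.

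A reader might also infer that 58.8% of the answers are not applicable. That too goes beyond the documents. No item-level n is given, and operators ask the questions, so blanks are possible. Day-only feeders may nap while feeding or read the stem loosely. SAP 6.0 gives the pattern at enrollment on the usual system, not on Mobility+. Only two daily Mobility+ feeds were required, so some of the 7 may have used it by day only.

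Finally, a subgroup defined by a Night-time tick in Appendix 8 would be open to objection. That tick is a post-baseline choice, and those who chose Mobility+ overnight may be those who liked it. The question also sits in a block covering the last three days, and night-time feeding does not prove feeding while asleep. This objection stands, and the fix avoids such a subgroup.

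**Conclusion.** The point holds as an interpretive defect of modest size. The item lacks a not-applicable option or rule, 10 of 17 participants had no usual night feed at baseline, and scores are averaged over the whole cohort. Its mean change, and its 1-in-9 or 1-in-10 part of the mobility score, therefore cannot be read as sleep during feeding.

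For the item alone the distortion can be large: 0.41 in place of 1.0 if day-only feeders do not change and all 17 answered. For the mobility score it is small, with size and sign resting on scores the documents do not give. The 7 with night feeds are an upper limit on those with a usual night feed at baseline who could also have rated sleep during feeding on Mobility+.

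**What to change.** In the SAP and study report:

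- Report any sleep-item comparison separately by baseline feeding time from Appendix 2 Q3 (7 with any night feed, 10 daytime only), with the number answering in each group.
- Base any statement about sleep during feeding on the 7 only, and label it descriptive.
- As a sensitivity analysis, give the mobility score as the mean of applicable items, with sleep left out for day-only feeders.
- Describe the Appendix 8 Mobility+ feeding times alongside, but do not select participants on them.

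An N/A box in Appendices 4 and 7 is worth adding for future use of the forms; it cannot alter answers already collected.

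The re-analysis needs no new data and little work, since feeding time was recorded at screening. The price is precision. With a two-sided 5% paired t-test (the SAP does not state sidedness), 80% power needs a mean change of about 1.27 SD with 7 participants, against 0.72 SD with 17. A non-significant result in the 7 would therefore say little.
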